8 CONVENTIONS

8.1 Calculations of Key Measures

8.1.1 IMACS DOI

IMACS DOI for the primary endpoint is defined as meeting all the following criteria:

- An improvement of $\geq 20\%$ in 3 IMACS core measures, AND
- No more than 2 IMACS core measure scores worsen by $\geq 25\%$, AND
- Manual Muscle Test (MMT-8) may not decrease by $\geq 25\%$.

For the exploratory analyses two modified IMACS DOI definitions will be considered:

First alternative definition

- A1: An improvement of $\geq 25\%$ in 3 IMACS core measures, AND
- A2: No more than 2 IMACS core measure scores worsen by $\geq 30\%$, AND
- A3: Manual Muscle Test (MMT-8) may not decrease by $\geq 30\%$.

Second alternative definition

- B1: An improvement of $\geq 30\%$ in 3 IMACS core measures, AND
- B2: No more than 2 IMACS core measures scores worsen by $\geq 35\%$, AND
- B3: Manual Muscle Test (MMT-8) may not decrease by $\geq 35\%$.

For the exploratory analyses the modified IMACS DOI definition using a 25% (and 30%) cutoff for improvement in 3 core measures, and no more than 2 core measures worsening by 30% (and 35%) and MMT-8 not decrease by 30% (and 35%) will be provided.

The IMACS Core measures are:

- Physician Global Assessment of Disease Activity (PGA).
- Patient (Subject) Global Assessment of Disease Activity (SGA).
- Manual Muscle Test (MMT-8).
- Health Assessment Questionnaire-Disability Index (HAQ-DI).
- Muscle Enzyme levels.
- Myositis Disease Activity Assessment Tool (MDAAT) Extramuscular Global Activity VAS (V-8 in the CRF).

8.1.2 Physician Global Assessment of Disease Activity (PGA)

Physician Global Assessment of Disease Activity (PGA) is measured using a 10cm visual analogue scale that can be performed by the investigator or sub-investigator.

8.1.3 Patient Global Assessment of Disease Activity (SGA)

Patient (Subject) Global Assessment of Disease Activity (SGA) is measured using a 10cm visual analogue scale that is performed by the subject.

8.1.4 Manual Muscle Test (MMT-8)

This tool assesses muscle strength using a 0-10 point scale. A set of 7 designated muscles is tested bilaterally plus axial (neck flexor) testing, so that the potential MMT-8 score ranges from 0-150.

The designated muscles tested will be:

- Neck flexors.
- Deltoid middle.
- Biceps brachii.
- Gluteus maximus.
- Gluteus medius.
- Quadriceps.
- Wrist extensors.

- Ankle dorsiflexors.

8.1.5 HAQ Disability Index

Scoring conventions for the Standard Disability Index of HAQ will be followed. The Standard disability index (HAQ DI) takes into account the subject's use of aids or devices or assistance in the scoring algorithm for a disability category. For each of the eight disability categories there is an AIDS OR DEVICES companion variable(s) that is used to record the type of assistance, if any, a subject uses for his/her usual activities. If aids or devices and/or assistance from another person are checked for a disability category, the score for this category is set to 2 (much difficulty), if the original score is 0 (no difficulty) or 1 (some difficulty). The HAQ DI is then calculated by summing the adjusted categories scores and dividing by the number of categories answered. Details of the HAQ DI scoring conventions are documented in "The Health Assessment Questionnaire".

8.1.6 Muscle Enzyme Levels

The muscle enzymes of interest are creatine kinase (CK), aldolase, AST, ALT, and LDH. To assess the DOI the most abnormal lab value (% above ULN) at baseline will be determined. The subsequent change from baseline for this lab value will be used to determine if the patient has met the criteria for the IMACS Definition of Improvement (DOI) at each time point. To assess the criteria for worsening, the change from baseline point will be determined for all 5 lab values at each time point indicated. The lab value with the greatest percent increase from baseline for each will be used to determine if the patient has met the criteria for worsening respectively (Section 3.1.5 of the Protocol).

8.1.7 Extramuscular Disease Activity using Myositis Disease Activity Assessment Tool (MDAAT)

This is a combined tool that captures the physician's assessment of disease activity of various organ systems using (1) a 0-4 scale and (2) a visual analog scale (VAS). It assesses the clinical features of each organ system based upon:

- The presence of clinical features or symptoms within the previous 4 weeks that are due to active disease (i.e., use your clinical judgment to determine how active the myositis associated clinical feature has been within the previous 4 weeks).
- The judgment that the feature is due to the myositis disease process (i.e., clinical findings known or suspected to be due to another disease process or due to therapy should NOT be considered in this evaluation).
- The concept that disease activity is defined as a potentially reversible finding.
- A clinical, functional, and laboratory assessment for each organ system.

The scoring system is based primarily on the physician's intention to treat (Categories A – D). In some cases, a patient may meet the clinical manifestations of a particularly category, but the treatment does not match the intention to treat of that particular category; in those cases, the category matching the clinical symptoms should be marked. If more than one clinical symptom is

present within a system, and different categories would be scored for each, mark the category that is most severe.

8.1.8 **IMACS Calculation**

IMACS DOI will be evaluable if there are at least 5 non-missing core measures, including MMT-8. In that case IMACS DOI status will be categorized as a response based on the available set of core measures satisfying the criteria mentioned above, otherwise, the status will be set as a non-response. If MMT-8 is not available or less than 5 core measures are available then IMACS DOI status will be subject to the imputation methods specified in Section 8.1.9.

Higher values for each component of the IMACS core measures (excluding MMT-8) indicate greater severity of disease. Improvement from baseline in a core measure of the IMACS will be computed as the difference between the baseline (Day 1 pre-treatment) value and the value at a given post-baseline visit. A positive value for improvement from baseline for an individual core measure indicates lesser severity of disease. The IMACS DOI will be defined based on the percent improvement from baseline in each of the IMACS core measure listed in [Section 8.1.1](#).

Percent improvement will be computed as the ratio of improvement from baseline to the baseline value times 100 for an endpoint:

$$\begin{aligned} \% \text{ Improvement} &= 100 * (\text{Improvement from Baseline}) / \text{Baseline Value} \\ &= 100 * (\text{Baseline Value} - \text{Post-baseline Value}) / \text{Baseline Value} \end{aligned}$$

For MMT-8, a higher value implies a lesser severity of disease; the % reduction in muscle strength will also be calculated as:

$$100 * (\text{Baseline Value} - \text{Post-baseline Value}) / \text{Baseline Value}$$

8.1.9 **Determination of IMACS DOI Responders**

Any subject who does not meet the IMACS DOI criteria is considered a non-responder. For IMACS DOI status that cannot be evaluated due to missing data (i.e. MMT-8 not available or less than 5 of the core measures available) the following conventions will be implemented:

- For the primary analysis at Week 24, any subject who prematurely discontinues the trial after receiving study medication will have missing data imputed as a IMACS/DOI non-responder at all scheduled protocol visits subsequent to the point of discontinuation. For the sensitivity analysis of the primary endpoint the data collection post discontinuation from the study will be used in the determination of the DOI status and included in the analyses. The tipping point sensitivity analysis will impute the missing data as described in [Section 7.5.3.2](#)
- Any subject for whom data are missing at a given visit not due to premature discontinuation will have a value for IMACS/DOI response imputed at that given visit. If the given visit is not the last scheduled efficacy visit (Day 169), imputation will depend on the observed responses from the previous scheduled visit and the next scheduled visit. If there are IMACS DOI responses observed at both visits, an IMACS DOI response will be imputed for the given

missing visit. Else, if a non-response is observed at one of the visits or a response is missing at one of the visits then a non-response will be imputed. If the given visit is the last scheduled efficacy visit (Day 169), the missing response will be imputed as non-response.

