The ULN is based on what is reported in the lab dataset for each enzyme.

Ranges for other core set measures:

Physician Global Assessment of Disease Activity (PGA) VAS: Range = 10

Patient Global Assessment of Disease Activity (SGA) VAS: Range = 10

Manual Muscle Testing (MMT-8): Range = 150

HAQ: Range = 3

Extramuscular Global Activity (using MDAAT): Range = 10

An improvement score is assigned for each core set measure based on the absolute percent change in the core set measure according to the definition in Table 2.1 above. These individual core set measure improvement scores are then totaled among the 6 core set measures to give the total improvement score.

A total improvement score between 0 and 100 corresponds to the degree of improvement, with higher scores corresponding to a greater degree of improvement.

APPENDIX 3 ANALYSIS PLAN FOR OPEN-LABEL, OPEN-LABEL EXTENSION AND LONG-TERM EXTENSION PERIODS ANALYSIS

Analyses specified in this section will be performed:

- 1) At the end of the open-label period, i.e. after all subjects have completed the 52-week assessment.
- 2) At the end of the open-label extension period, i.e. after all subjects have completed the 76-week assessment (Japan sites only).
- 3) At the end of the long-term extension period, i.e. after all subjects have completed the 3-year assessment and all protocol specified follow-up visits.

For sections “Background and Rationale; Study Description; Objectives; Endpoints; Sample Size and Power; Study Periods, Treatment Regimens and Populations for Analyses; Conventions” and their subsections, see [Section 1-Section 6](#) and [Section 8](#) of SAP for 24-week analysis of the double-blind study period. Any changes or modification to the analysis for the double-blind period will be explicitly presented.

The open-label analysis will include safety assessment for all safety data in the database at the time of the 52-week database lock.

The open-label extension analysis will include safety assessment for all safety data in the database at the time of the 76-week database lock.

The long-term extension analysis will include safety assessment for all safety data in the database at the time of the study final database lock.

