11.6.1 Other Efficacy Analyses

IMACS DOI

Proportion of subjects in IMACS DOI over time during the study will be presented by the double-blind treatment groups and visit. Point estimate of response rate, 95% CI, point estimates and 95% CI of treatment difference adjusted for randomization stratification factors: disease diagnosis (DM vs. Non-DM), ILD (absent vs present), Region (Japan vs ROW) (based on minimum risk weights).

Proportion of subjects who meet the $\geq 20\%$ improvement from baseline over time for each of the core measures of IMACS (PGA, SGA, MMT-8, HAQ-DI, MDAAT and muscle enzymes) will be presented by double-blind treatment groups and visit. Point estimate of response rate, 95% CI, point estimates and 95% CI of treatment difference adjusted for randomization stratification factors: disease diagnosis (DM vs. Non-DM), ILD (absent vs present), Region (Japan vs ROW) (based on minimum risk weights).

The proportion of subjects in IMACS Minimal, Moderate and Major responses using the Myositis Response Criteria tool (as defined in [section 8.1.11](#)) will also be presented over time during the study. Point estimates and 95% CI within each treatment group for IMACS Minimal, Moderate and Major DOI response will be provided by visit. Differences in IMACS Minimal, Moderate and Major DOI response rates between the double-blind treatment groups will be provided by point estimate and corresponding 95% CIs based on an ordinal logistic regression model.

Additional separate longitudinal repeated mixed effects models will be used to assess the mean change from baseline over time in the study in each of the IMACS core measures (PGA, SGA, MMT-8, HAQ-DI, MDAAT and muscle enzymes). The mixed models will include double-blind treatment group, baseline measurement, randomization stratification factors: disease diagnosis (DM vs. Non-DM), ILD (absent vs present), Region (Japan vs ROW), time (study days in which each core measure was collected), time by baseline measurement and time by treatment interactions as fixed effects and subject as a random effect. Adjusted mean, SE, 95% CI for adjusted mean difference between treatment groups will also be provided. The estimate of baseline mean core measure, mean post-baseline core measure, and adjusted mean change from baseline core measure will be also be presented by double-blind treatment group and visit.

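### As printed, SAP 8.1.8 gives MMT-8 improvement the wrong sign in criterion 1 of the primary endpoint, and no other MMT-8 improvement formula is given

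*SAP*

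**What the plan says.** SAP 8.1.1 sets three DOI criteria: (1) at least 20% improvement in three core measures; (2) at most two core measures worse by 25% or more; (3) "Manual Muscle Test (MMT-8) may not decrease by" 25% or more. MMT-8 is one of the six listed core measures. The section then adds: "For the exploratory analyses two modified IMACS DOI definitions will be considered". These raise the improvement threshold to 25% and 30%, and the worsening and MMT-8 limits to 30% and 35%.

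SAP 8.1.8 notes that on every core measure except MMT-8 a higher value is worse. It continues:

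- How change is computed: "Improvement from baseline in a core measure of the IMACS will be computed as the difference between the baseline (Day 1 pre-treatment) value", from which a later visit's score is subtracted.
- What the sign means: "A positive value for improvement from baseline for an individual core measure indicates lesser severity of disease".
- How the endpoint uses it: "The IMACS DOI will be defined based on the percent improvement from baseline in each of the IMACS core measure listed in" SAP 8.1.1.
- The expression printed for that percentage: 100 × (baseline − post)/baseline.
- For MMT-8, after recognising that higher is better: "the % reduction in muscle strength will also be calculated as", followed by the same expression, 100 × (baseline − post)/baseline.

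No formula for percent worsening is printed. Protocol 5.4.1.1 repeats the three thresholds without any formula.

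SAP Appendix 3 refers back to Section 8 for its conventions and adds: "Any changes or modification to the analysis for the double-blind period will be explicitly presented". Its section 11.6.1 reports the proportion of subjects with at least 20% "improvement from baseline over time for each of the core measures of IMACS (PGA, SGA, MMT-8, HAQ-DI, MDAAT and muscle enzymes") and gives no different MMT-8 formula.

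SAP Appendix 2 scores the Myositis Response Criteria (MRC) from 100 × (post − baseline)/range for all six measures. The result is looked up in bands labelled as worsening or improvement (Table 10-2).

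**The concern.** The general formula treats a fall in score as improvement. That is right for five of the six core measures and backwards for MMT-8. The one line written for MMT-8 does not reverse it: it repeats the expression under another name. Within a single paragraph, the words say that positive means less severe disease, while the formula gives a weaker patient a positive value.

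This paragraph is the written derivation of criterion 1 of the primary endpoint. MMT-8 is also the one measure that 8.1.8 requires before the DOI can be evaluated at all, so the rule enters every evaluable determination. The modified DOI definitions and the per-measure proportions in 11.6.1 inherit it.

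**Working it through.** The plan prints no worked example for this rule, so the check is direct substitution.

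**Inputs.** The DOI criteria are from SAP 8.1.1 and the formula from SAP 8.1.8. The MMT-8 maximum of 150 is from SAP 8.1.4, and entry at MMT-8 of 135 or below from Protocol 3.3.1. The patient values are illustrative.

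**Formulas for MMT-8.**
- Printed: 100 × (baseline − post)/baseline.
- Direction implied by the words: 100 × (post − baseline)/baseline.

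**Illustrative patient.** PGA and SGA each go from 5 to 4, so 100 × (5 − 4)/5 = 20% improved on both. HAQ-DI, enzyme and extramuscular activity are unchanged. Criterion 2 uses the percent reduction for MMT-8 and is met throughout.

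| MMT-8 | % improvement, printed | % improvement, intended | Measures improved, printed / intended | Criterion 3 | Status, printed / intended |
|---|---|---|---|---|---|
| 100 to 120 | −20 | +20 | 2 / 3 | met | non-responder / responder |
| 100 to 80 | +20 | −20 | 3 / 2 | met (20% fall) | responder / non-responder |
| 100 to 76 | +24 | −24 | 3 / 2 | met (24% fall) | responder / non-responder |
| 100 to 75 | +25 | −25 | 3 / 2 | not met | non-responder / non-responder |

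**How far it can reach.**
- *Lost responders.* A gain of 20% needs a baseline of at most 150/1.20 = 125. From 135, the largest gain is 15/135 = 11.1%.
- *False responders.* The fall must be at least 20% but under 25%, because criterion 3 blocks larger falls. The whole-number later scores are 76–80 from a baseline of 100, 94–100 from 125, and 102–108 from 135.
- *Criterion 3.* Correct as printed, because a percent reduction is what it needs.
- *Criterion 2.* Correct if the percent reduction is used for MMT-8. It goes wrong only if worsening is taken as the negative of the printed improvement: 100 to 125 would then be −25% and count as worse.

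**Where the formula is inherited.**
- *Modified definitions.* From a baseline of 100, the false-responder windows are 71–75 (fall of 25% to under 30%) and 66–70 (30% to under 35%). Lost responders need a baseline of at most 150/1.25 = 120 or 150/1.30 = 115.4.
- *Section 11.6.1.* Criterion 3 plays no part here, so 100 to 70 would be reported as a 30% improvement.

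**Appendix 2 (secondary).** The band maxima sum to 20 + 10 + 32.5 + 10 + 7.5 + 20 = 100, which reproduces the stated 0–100 range. Under the printed change formula:
- MMT-8 100 to 120 gives (120 − 100)/150 = +13.3%, which fits its improvement band (20 points).
- PGA 5 to 3 gives (3 − 5)/10 = −20%, although the band labels plainly intend an improvement (15 points).

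The formula's sign agrees with the bands only for MMT-8.

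**The case against.** The strongest reply is that 8.1.8 sets MMT-8 aside at the start and returns to it separately at the end, so the general formula may be meant only for the other five measures. That reading is open. However, the exclusion sits in the sentence about severity, not in the one giving the formula; the DOI is tied to percent improvement in each listed measure; and the MMT-8 line adds a further calculation without replacing the first. If the exclusion does carry over, the SAP has no MMT-8 improvement formula at all. Criterion 1 lacks a usable rule either way.

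The second reply is that the intent is obvious: positive is said to mean less severe, and criterion 3 treats an MMT-8 fall as harm. This stands, and it limits the point to a correction of the text. The patient examples show what the formula does if followed literally; they do not estimate how often that would happen. The modified definitions are exploratory and 11.6.1 carries no p-values, so they show where the formula travels and add little weight.

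A reader might infer that Appendix 2 leaves the MRC score undefined. The documents do not support that: the band labels show what counts as improvement, and 8.1.8 gives the direction of the five measures concerned. That part is a clarification only.

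**Conclusion.** The point holds as an error in a written rule. Followed as printed, SAP 8.1.8 counts strength loss as MMT-8 improvement in criterion 1 and contradicts its own sentence on what a positive value means; on the alternative reading it gives no MMT-8 improvement formula. Individual classifications can reverse in both directions, within the limits shown: gains of 20% or more from a baseline of 125 or below, and falls of 20% to under 25%. It should be fixed because it concerns the primary endpoint. The Appendix 2 gap is minor, though it concerns the secondary endpoint ranked second in SAP 7.5.1.

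A reader might infer that the analysis was programmed with the wrong sign, or that response rates or power are off. The documents support neither: they contain no program, the intended direction is clear from the words, and the sample size rests on assumed response rates that do not use this formula. A reader might also infer that criterion 2 is reversed. That needs an added assumption about how worsening is computed, which the SAP does not print.

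**What to change.** In SAP 8.1.8, state that for MMT-8, % improvement = 100 × (post − baseline)/baseline. Keep the percent reduction for the criterion 3 check, and state that it also measures MMT-8 worsening in criterion 2. The modified definitions and 11.6.1 then follow without further change.

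Leave enzyme worsening in the DOI as it is. The rule in SAP 8.1.6 that takes the largest increase among the five enzymes points to Protocol 3.1.5, which covers rescue; bringing it into the DOI would be a separate change to the primary endpoint.

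In Appendix 2, add one sentence: improvement is 100 × (baseline − post)/range for PGA, SGA, HAQ, enzyme and extramuscular activity, and 100 × (post − baseline)/range for MMT-8.

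Check that the program specifications match. The cost is a few lines of SAP text and that check. No new data are needed, and neither the design nor the sample size changes.

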## 8 STATISTICAL CONSIDERATIONS

### 8.1 Sample Size Determination

A sample size of 150 subjects (75 subjects per treatment group) is planned based on the primary comparison of the proportion of subjects with IMACS DOI (as defined under the primary objective) at Day 169 (Week 24) between the SC abatacept group and the placebo group on a background of standard treatment.

A sample size of 150 subjects randomized in a 1:1 ratio to the SC abatacept group and placebo group will yield a power of approximately 90% to detect a treatment difference of 27% in the rate of IMACS DOI between the 2 treatment groups based on a continuity corrected chi-squared test. This power estimate assumes a two-sided alpha level of 5%, IMACS DOI rate of 60% in the abatacept group and 33% in the placebo group.

The 60% estimate of IMACS DOI in the abatacept group was based on reported rates of IMACS DOI in studies of patients with Myositis on combination therapy with another biologic agent. It is expected that the rate of IMACS DOI on abatacept in combination with standard treatment should be similar to that observed with the use of another biologic agent in combination with standard treatment. Table 8.1-1 below presents the power estimates for other considerations of proportion of subjects in IMAC DOI in the abatacept group assuming the total sample size of 150 subjects. Randomization will be stratified globally by 3 stratification variables: (1) disease diagnosis (Dermatomyositis [DM] vs non-DM IIM), (2) Interstitial Lung Disease (ILD) (present vs absent), (3) Japan vs ROW.

Table 8.1-1: Estimates of Power for Various Assumed Rates of IMACS DOI at Week 24 Assuming Total Sample Size of 150			
Aba Rate	Placebo Rate	Delta	Power (%)
50%	20%	30%	96
	25%	25%	85
55%	25%	30%	95
	30%	25%	84
60%	25%	35%	~ 99
	30%	30%	95
	35%	25%	83

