3.4.2.1 Prohibited Medications	Added text 'All prohibited medication must have been discontinued at least 4 weeks prior to randomization with the exception of immune globulin, rituximab and d-penicillamine which have longer exclusion periods (see 3.3.2). Prohibited medication in this contest refers to immunomodulatory medications for the treatment of IIM which are not included as immunosuppressant medications (Section 3.4.1.3). The following list includes examples of specific prohibited medications.'  Also added/removed several therapies.	
3.4.2.2 Restricted Medications	Developed second bullet-point.	
3.5 Discontinuation of Subjects following any Treatment with Study Drug	Second paragraph: Provided substantial text revision to clarify the requirements for subjects that discontinue	
Table 4-1: Study Drugs for IM101611	Added 'Open Label'.	
Table 5.1-2 Study Evaluations - Double-Blind Period (IM101611)	Added Wk 8 assessments for MMT-8 & MDAAT	
Table 5.1-5	Revised Schedule/T&E 'Title'.	
5.4.1.2 Assessments Performed by Medical Staff: Myositis Response Criteria	Added a 'continuous total improvement score' range '0-100'.	
Table 5.5.1-1 Sampling Schedule	Amended Study Days to reflect '85 Days & 169 Days after Last Dose	
6.1.1 Serious Adverse Event Collection and Reporting	Text revised to clarify the reporting of SAEs and Pregnancies immediately.	

Summary of Key Changes of Revised Protocol 03		
Section Number & Title	Description of Change	
[REDACTED]	[REDACTED]	[REDACTED]
8.4.7 Final Study (Week 52) Analysis	Amended [REDACTED] Section 8.4.7 to reflect 85 days and 169 days post last dose in study	[REDACTED]
8.4.2.1 Primary Efficacy Analysis & Table 8.4.2.2-1 Planned Efficacy Analyses	Replaced 'IMACS score' with 'MMT8, baseline MDAAT, baseline PGA'. Clarifying also 'Time to event (IMACS DOI at 2 consecutive time points) up to Day 169 (Week 24)'	[REDACTED]
11. LIST OF ABBREVIATIONS	Additional abbreviations added.	[REDACTED]
[REDACTED]	[REDACTED]	[REDACTED]
Throughout Revised Protocol 03	Amended 'anti-TIF1-c' 'to anti-TIF1-γ'.	[REDACTED]
Throughout Revised Protocol 03	Grammatical and spelling corrections throughout the document. Also addition of other minor clarifications and correction of typographical errors.	[REDACTED]

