7.1 General Methods

The table below provides an overview of the efficacy analyses to be performed. These are thought to be robust in the case of the small marginal strata (Japan) frequencies of 20 or more (10 per treatment group); otherwise, some strata may be dropped from the models.

Table 7.1-1: Planned Efficacy Analyses

Measure of Interest	Analysis Method
IMACS DOI at Day 169 (Week 24)	
Primary Analysis:
 Using a logistic regression model that includes treatment group, stratification factors: disease diagnosis (DM vs. Non-DM), ILD (absent vs. present), Region (Japan vs. ROW), baseline MMT8 score, baseline MDAAT, and baseline PGA. Point estimate of adjusted ORs, corresponding 95% CI and p-value will be provided. The proportion of subjects in IMACS DOI in each treatment group and corresponding 95% CI will also be provided.
Time to event (IMACS DOI at 2 consecutive time points) up to Day 169 (Weeks 12 and 24)	Point estimates and 95% CIs for the hazard ratio of abatacept versus placebo will be based on Cox proportional hazards models. The stratification factors: disease diagnosis (DM vs. Non-DM), ILD (absent vs. present), Region (Japan vs. ROW), baseline MMT8 score, baseline MDAAT and baseline PGA will be included in the model. Observations from subjects who discontinue due to lost to follow-up will be censored at the date of last available data in the study. The date of the first IMACS DOI of the 2 consecutive IMACS DOI events will be used in the analysis. Estimate the distribution of time to first occurrence of event using Kaplan-Meier method/curve.
Changes from baseline in continuous variables (i.e., FI-2 scores, MRC total improvement score, IMACS core components, XXXXXXXXXX)	Longitudinal (repeated measures) model [including treatment group, baseline value of variable and randomization stratification factors: disease diagnosis (DM vs. Non-DM), ILD (absent vs. present), Region (Japan vs. ROW), time (categorical as study visit at which variable was measured), time by baseline value of variable and time by treatment as fixed effects and subject as a random effect], adjusted mean, SE, 95% CI for adjusted mean difference between treatment groups will be provided for all time

Table 7.1-1: Planned Efficacy Analyses

Measure of Interest	Analysis Method
	points. In addition, nominal p-values will be provided for the secondary endpoints of change from baseline at Day 169 (week 24) analysis.

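### Week 8 DOI was not measurable before Revised Protocol 03, yet SAP 8.1.9 imputes it, mostly as non-response, which lowers the pooled Day 57 DOI rate

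*SAP*

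**What the plan says.** The protocol's summary of key changes for Revised Protocol 03 (Appendix 4) records against Table 5.1-2: "Added Wk 8 assessments for MMT-8 & MDAAT". The document history dates that revision 09-May-2018, 22 months after the original protocol of 08-Jul-2016. The current Table 5.1-2 schedules both assessments at Day 57.

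SAP 8.1.8 sets the condition for scoring DOI at a visit: "IMACS DOI will be evaluable if there are at least 5 non-missing core measures, including MMT-8". It then says: "If MMT-8 is not available or less than 5 core measures are available then IMACS DOI status will be subject to the imputation methods" set out in SAP 8.1.9.

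SAP 8.1.9 covers any visit with missing data that is not due to premature discontinuation. For a visit before Day 169 it looks at the scheduled visits on either side. Two observed responses give an imputed response, but "if a non-response is observed at one of the visits or a response is missing at one of the visits then a non-response will" follow. A missing Day 169 is a non-response whatever the neighbouring visits show.

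The visible text makes no exception for an assessment that the protocol version in force did not ask for. SAP 2.4 lists Revised Protocol 03, and the legible part of its entry does not mention Week 8.

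**The concern.** The change log matters here only as evidence of when data collection began; nothing in it conflicts with the current protocol text. Before the change, Week 8 could supply at most the two global assessments, HAQ-DI and the muscle enzymes. That is 4 of 6 measures without MMT-8, so both conditions of SAP 8.1.8 fail by design.

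The SAP then treats a measurement nobody was asked to make as ordinary missing data and gives it a response status. Subjects seen later are scored on what was measured. The Day 57 DOI rate therefore mixes two definitions, in proportions set by when subjects were enrolled. At stake is a faithful picture of early response and of the early difference between arms.

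There is one knock-on effect. If Day 85 is missing in such a subject, its earlier neighbour (Day 57) was never observed, so Day 85 is always imputed as non-response, even when Days 29 and 113 are both responses.

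**Working it through.** **Plan figure.** The plan gives no figure for Week 8 DOI. The nearest one is the power statement: 75 per arm "will yield a power of approximately 90% to detect a treatment difference of 27" percentage points. With the continuity correction, d = 0.27 and effective n = 75 − 2/d + 1/(75d²) = 75 − 7.41 + 0.18 = 67.8 per arm, which gives 89.2% power. Exact enumeration of the corrected test gives 90.3%. The figure reproduces. It serves below only to anchor the Week 24 rates at 60% and 33%.

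**What the rule does.** Write R4, R8, R12 for response (1) or not (0) at Weeks 4, 8 and 12. For an affected subject the imputed R8 is R4 × R12.

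| R4-R8-R12 | True Week 8 | Imputed Week 8 |
|---|---|---|
| 1-1-1 | response | response |
| 0-1-1, 1-1-0, 0-1-0 | response | non-response |
| 1-0-1 | non-response | response |
| 0-0-0, 0-0-1, 1-0-0 | non-response | non-response |

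So p_imp = P(R4 = 1 and R12 = 1) ≤ min(p4, p12). This bound needs no modelling. The error is p8 − p_imp = P(0-1-1) + P(1-1-0) + P(0-1-0) − P(1-0-1). It runs both ways, and its net sign depends on the rates.

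**Size on assumed rates.** The documents give no early DOI rates. Three assumed sets ending at 60% and 33% at Week 24 were simulated, with 400,000 subjects per arm and within-subject latent correlation of 0.5, 0.7 and 0.9. Ranges run from correlation 0.5 to 0.9.

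| Set, arm | Assumed Wk 4/8/12 | Wk 8 imputed | Imputed as non-response |
|---|---|---|---|
| Low, abatacept | 10/22/33% | 6.9–9.8% | 93–90% |
| Low, placebo | 6/12/18% | 3.2–5.7% | 97–94% |
| Middle, abatacept | 20/33/43% | 14.4–19.5% | 86–81% |
| Middle, placebo | 12/19/24% | 6.8–11.1% | 93–89% |
| High, abatacept | 35/45/50% | 25.2–33.1% | 75–67% |
| High, placebo | 20/25/28% | 11.0–17.6% | 89–82% |

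Of true Week 8 responders, 14 to 69% keep that status. The net effect is downward in every set.

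**Pooling.** With affected share s, the pooled rate is (1 − s) × p8 + s × p_imp. For the middle set on abatacept:
- s = 10%: 29.7 + 1.4 to 29.7 + 2.0 = 31.1 to 31.7%
- s = 30%: 23.1 + 4.3 to 23.1 + 5.9 = 27.4 to 29.0%
- s = 50%: 16.5 + 7.2 to 16.5 + 9.8 = 23.7 to 26.3%

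All are below 33%. If s is equal in both arms, the 14-point difference (33 − 19) at Day 57 becomes, at s = 30%, 0.7 × 14 + 0.3 × 7.6 = 12.1 to 0.7 × 14 + 0.3 × 8.4 = 12.3 points.

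**Shape of the curve.** The pooled Week 8 rate falls below the Week 4 rate only if s > (p8 − p4)/(p8 − p_imp). For middle-set abatacept that is 13/18.6 = 70% to 13/13.5 = 96%. The lowest threshold in the table is high-set placebo at correlation 0.5: 5/14 = 36%. Flattening is the usual result; a dip needs a large affected share.

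**The case against.** The strongest case is that the affected result cannot be seen. The detailed exploratory efficacy text after SAP 7.5.4 is blacked out and may leave unscheduled Week 8 values out. The DOI-over-time analysis that is visible, in Appendix 3 (SAP 11.6 and 11.6.1), is as observed without imputation, which already keeps these subjects out of the Day 57 denominator. SAP 8.3 also flags imputed DOI values in listings. All of this stands. Even so, SAP 8.1.9 sets a rule for visits before Day 169, and as written it reaches Day 57.

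The affected share may be small or nil. That also stands: without it the size is unknown.

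Four stronger readings are tempting, and the documents do not support them.

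- **The rule delays time to DOI.** If Days 29 and 85 are both observed, the rule gives the same event dates as simply treating them as adjacent visits: (1,1) gives an event at Week 4; (0,1) gives Week 12 at the earliest; (1,0) and (0,0) give none starting at Week 4 or 8. What is lost is lost because Week 8 was not measured. The SAP row is also labelled "Time to event (IMACS DOI at 2 consecutive time points) up to Day 169 (Weeks 12 and 24", where the bracket closes. If that limits the visits used, Week 8 never enters. In the simulation, confirmed DOI at any time by Week 24 changes by at most about 2.4 points.
- **The curve must dip at Week 8.** It need not, as the threshold above shows.
- **A mismatch with Appendix 3 would prove the error.** Appendix 3 uses another population and no imputation, so its rates can differ at any visit with missing data.
- **The trial's main conclusions are biased.** The primary endpoint uses Day 169, whose missing-data rule ignores neighbouring visits. The four ranked secondary endpoints (SAP 7.5.1) do not use DOI imputation. Randomisation should roughly balance enrolment era between arms, so the expected effect is dilution, not a false positive.

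**Conclusion.** The point holds within narrow limits. For subjects whose Day 57 visit preceded the Week 8 change at their site, the visible SAP imputes a DOI status that could not be measured and caps the rate at the lower of its neighbours. On the assumed rates, 67 to 97% of these values become non-responses, a minority are wrongly made responses (pattern 1-0-1), and the pooled Day 57 rate is pulled down.

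The size scales from nothing at a zero share to the full gap in the table if everyone is affected. The conclusion assumes that sites did not record MMT-8 and MDAAT at Week 8 before being asked to, and that no blacked-out text makes an exception. It concerns exploratory by-visit results that are not formally tested. It is worth correcting because it is avoidable and cheap, not because it threatens the trial's main inference.

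**What to change.** Add to SAP 8.1.9: where MMT-8 and MDAAT were not scheduled at Day 57 under the protocol version in force at the site, Day 57 DOI is treated as not scheduled. It is not imputed, and the subject is not in the Day 57 denominator. For these subjects, Day 29 is the previous scheduled DOI visit when a missing Day 85 is imputed.

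This needs one derived flag, based on when Revised Protocol 03 took effect at each site rather than on its issue date. Reporting the number flagged per arm would show at once whether the issue matters. No change to the Cox model is needed, and the wording should not be presented as restoring event dates. The cost is a smaller Day 57 denominator. Study procedures and the primary analysis do not change.
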